8.3 ESTIMATED STUDY DATES

- Protocol Planned Date: October 2018
- First Patient In (FPI): December 2018
- Last Patient In (LPI): March 2019
- Last Patient Out (LPO): December 2019
- Estimated enrollment duration: 3 Months
- Estimate treatment duration: 9 Months
- Database lock planned date: January 2020
- Estimated Report date: February 2020

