16.3 STUDY ENDPOINTS

During interim analysis (at 6 months of treatment) and final analysis at the end of treatment, the following endpoints will be evaluated:

16.3.1 Primary Efficacy Endpoint:

- Compare the mean relative change in ALT & AST levels between the experimental arms and the control arm.
- Compare proportions of patients with normal ALT & AST at end of treatment between the experimental arms and the control arm. The cut-off values of ALT were 0-43 IU/L and of AST were 0-40 IU/L⁷.

16.3.2 Secondary Efficacy Endpoints:

- Comparing the mean change in Fib-4 score between the experimental arms and the control arm.
- Comparing the frequency and percentage of patients experiencing hepatic complications

⁶ Gpower 3.1

⁷ Uslusoy H, Nak S, Gülten M, Bıyıklı Z. Non-alcoholic steatohepatitis with normal aminotransferase values. World Journal of Gastroenterology. 2009;15(15):1863.

between the experimental arms and control arm.

16.3.3 Exploratory Endpoint:

- Compare the mean relative change in lipid profile levels between the experimental arms and the control arm.

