- The mean change in Fib-4 score between the experimental arms and the control arm from baseline till end of treatment using T-test (Mann-Whitney test in case of non-parametric data). This analysis will be a comparative analysis and will be done on eligible population of patients without protocol violation and who have at least one treatment dose and an evaluable primary endpoint (AST and ALT).
- Number of patients experiencing hepatic complications between the experimental arms and control arm at the end of the treatment using chi-square (Fischer for non-parametric data). This analysis will be a comparative analysis and will be done on eligible population of patients without protocol violation and who have at least one treatment dose and an evaluable primary endpoint (AST and ALT).

16.4.4 Exploratory analysis:

- The mean relative change in lipid profile levels between the experimental arms and the control arm from baseline till end of treatment using T-test (Mann-Whitney test in case of non-parametric data). This analysis will be a comparative analysis and will be done on eligible population of patients without protocol violation and who have at least one treatment dose and an evaluable primary endpoint (AST and ALT).

16.4.5 Interim analysis:

- Interim analysis will be performed when all patients complete 6 months of treatment. If a statistically significant difference is observed between placebo and active arm(s), the study will be terminated for the benefit of patients who were randomly assigned to placebo arm and to rapidly disseminate evidence supporting a treatment benefit to the broader community⁹.

⁹Zannad F, et al. Development of Therapeutics for Heart Failure. When to Stop a Clinical Trial Early for Benefit: Lessons Learned and Future Approaches. *Circulation: Heart Failure*. 2012; 5: 294-302. doi: 10.1161/CIRCHEARTFAILURE.111.965707

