19 PREMATURE DISCONTINUATION OF THE STUDY OR PREMATURE CLOSE-OUT OF A SITE

The sponsor may discontinue the study or close-out a site in some cases e.g.;

- If the information on the product leads to doubt as to the benefit/risk ratio;
- If the Investigator has received from the Sponsor all Investigational Product, means and information necessary to perform the Clinical Trial and has not included any patient after a reasonable period of time mutually agreed upon;
- If results of interim analysis show a statistically significant difference between placebo and active arms (in favor of active arm), the study will be terminated for the benefit of patients who were randomly assigned to placebo arm and to rapidly disseminate evidence supporting a treatment benefit to the broader community;
- If the aim of the Clinical Trial has become outdated or is no longer of interest;
- In the event of breach by the Investigator of a fundamental obligation under this agreement, including but not limited to breach of the Clinical Trial Protocol, breach of the applicable laws and regulations or breach of the ICH guidelines for Good Clinical Practice.

In any case, the Sponsor will inform the appropriate Ethics Committee(s) (IRB/IEC) and Health Authorities. In addition, investigators should be notified by written notice.

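### The 6-month efficacy stop can spare a placebo patient at most 12 weeks, and as written it puts the week-36 endpoint data at risk

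*Protocol*

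**What the plan says.** **The look.** Section 16.4.5 of the protocol, and the synopsis, state: "Interim analysis will be performed when all patients complete 6 months of treatment". A statistically significant difference between placebo and an active arm then ends the study. The third bullet of section 19 repeats the consequence and the main reason for it: "the study will be terminated for the benefit of patients who were randomly assigned to placebo arm". All three places add a second aim, early publication of evidence of benefit. The list in section 19 opens permissively, but the bullet itself and 16.4.5 make termination obligatory.

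**The calendar.** Section 8.3 gives "First Patient In (FPI): December 2018", "Last Patient In (LPI): March 2019", "Last Patient Out (LPO): December 2019", "Estimated enrollment duration: 3 Months" and "Estimate treatment duration: 9 Months". Section 8.1 gives the same plan as 12 weeks of recruitment and 36 weeks of treatment.

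**The endpoints.** Section 16.3 sets as a primary endpoint: "Compare proportions of patients with normal ALT & AST at end of treatment between the experimental arms and the control arm". Section 16.4 also measures the relative change in ALT and AST to the end of treatment, and places the final analysis at 9 months. In the section 2 schedule, week 36 is the only visit after week 24. It includes ALT/AST, FibroScan, Fib-4, lipids and adverse events. Section 16.2 applies last observation carried forward.

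**What is not stated.** The protocol does not say how long the interim takes from data cut to decision, whether week-36 visits go ahead after a stop, or whether any patient receives Heptex afterwards.

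**The concern.** This point is about when the look happens and what follows from it, not about its significance level. The look waits for the last patient to reach 6 months. By then recruitment has been over for six months, so a stop keeps nobody from being randomised to placebo. It can only shorten courses that are already well advanced. No passage provides Heptex to placebo patients after a stop. With 1:1:1 allocation, the stop would also cut short the two active arms (94 patients planned, against 47 on placebo).

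At stake is the question that the trial defines as primary, the 9-month result. If follow-up ends at the stop, the week-36 enzymes, FibroScan, Fib-4, lipids and safety data are missing for the later enrolees. If the carry-forward rule is then applied, the end-of-treatment value is week 24 for those patients and week 36 for the early ones.

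**Working it through.** **1. Reproduce the plan's own date.** Last patient in, March 2019, plus 9 months gives December 2019, which is the stated last patient out. The section 8.3 dates therefore track treatment time.

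**2. Locate the look.**
- Trigger: March 2019 + 6 months = September 2019.
- First patient's end of treatment: December 2018 + 9 months = September 2019.
- In study weeks: the last patient's week 24 is 12 + 24 = 36, which is the first patient's week 36.

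The days within the months are not given. Taking the extremes of December and March, the first patient is between week 32.6 and week 41.1 at the trigger.

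**3. The most that can be spared.** At the trigger, every patient on schedule is at week 24 or later, so nobody has more than 36 − 24 = 12 weeks left. This needs no assumption about accrual or lag.

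**4. Mean spared and data lost.** Assumptions: entry is even over the 12 weeks, the decision takes L weeks from the trigger, treatment and visits continue meanwhile, and there is no dropout.
- Mean treatment left per patient = (12 − L)² / 24 weeks.
- Share not yet at week 36 = (12 − L) / 12.

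The protocol gives no value for L. Its final-analysis timeline allows about one month from last visit to database lock and about two to the report. I use 4 and 8 weeks as a proxy.

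| L (weeks) | Mean weeks spared | Share of 36 weeks | Week-36 assessments lost if follow-up ends |
|---|---|---|---|
| 0 | 144/24 = 6.0 | 16.7% | nearly all of 141 |
| 4 | 64/24 = 2.7 | 7.4% | 8/12 = 67% (94 of 141) |
| 8 | 16/24 = 0.7 | 1.9% | 4/12 = 33% (47 of 141) |
| 12 | 0 | 0% | none |

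Across the 47 placebo patients, L = 0 spares 47 × 6 = 282 of 47 × 36 = 1,692 planned patient-weeks.

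**5. Sensitivity to accrual shape.** The ranges below run from front-loaded to back-loaded (triangular) entry.
- L = 0: 4.0 to 8.0 weeks spared.
- L = 4: 1.2 to 4.2 weeks spared, 44% to 89% of week-36 data lost.
- L = 8: 0.15 to 1.2 weeks spared, 11% to 56% lost.

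**The case against.** The best defence is that this is a deliberate choice. The look uses complete week-24 data, and ALT/AST, FibroScan, Fib-4 and lipids are all scheduled at that visit. The decision therefore rests on a common time point. Early publication is a second stated aim, and a stop would serve it. Loss of data by enrolment date does not favour any arm by design, because patients are randomised. The loss is also inferred: no passage says that week-36 visits would be cancelled, and an analysis plan not shown may deal with this.

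Much of that stands, and it rules out several stronger readings.
- A reader might infer that stopping spares almost nothing, or that few patients are still on placebo. The dates do not show this. With no lag the mean is 6 weeks and the last entrant has 12. After 4 weeks two thirds are still on treatment. Only a lag of about 8 weeks makes the saving negligible, and that lag is borrowed from the final-analysis timeline.
- A reader might add the worst case of each harm together. They do not occur together: near-total data loss goes with 6 weeks spared, and 0.7 weeks spared goes with a one-third loss.
- A reader might infer that the interim mixes time points or biases the comparison. Neither follows. Mixing arises only if a stopped trial is later analysed with week-24 values carried forward beside week-36 values.

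The rule itself is not rescued. It is obligatory as written, its only safeguard for the 9-month data is silence, and the gain to placebo patients is bounded at 12 weeks.

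**Conclusion.** The point holds in a bounded form. By the protocol's own calendar, the mandatory stop comes after enrolment has closed and as the first patients finish. It can spare a placebo patient 12 weeks at most, 6 on average with an immediate decision, and about 2.7 or 0.7 with a 4- or 8-week turnaround. If follow-up ends with the stop, the price is the week-36 data of nearly all, 67% or 33% of patients respectively.

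The 12-week bound rests on the stated schedule alone. The averages and percentages also rest on even accrual and an assumed lag, and the loss rests on follow-up ending, which the protocol leaves open. The harm is loss or blurring of the defined 9-month endpoint, not imbalance between arms. The protocol should be changed, because the gain is small and the safeguard needs only wording.

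**What to change.** In the synopsis, section 16.4.5 and the third bullet of section 19, remove termination as the consequence of a significant interim result. Keep week 24 as a planned, non-stopping analysis, and take the primary result at week 36 in all patients.

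If the sponsor wishes to keep an early look with consequences, the minimum is to state two things: all patients complete the week-36 assessments, and the week-36 analysis remains primary whatever the interim shows.

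Either change is wording only, with no added patients or visits. The cost is that the definitive result, and the early publication that the protocol also wants, come at most about two to three months later.

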- Number of patients with normal ALT & AST at end of treatment between the experimental arms and the control arm. The cut-off values of ALT were 0-43 IU/L and of AST were 0-40 IU/L⁴ using chi square (Fischer test for non-parametric data). This analysis will be comparative analysis and will be conducted on the eligible population of patients without protocol deviation, who have at least one treatment dose and an evaluable primary endpoint (ALT and AST).

Secondary Analysis:

- The mean change in Fib-4 score between the experimental arms and the control arm from baseline till end of treatment using T-test (Mann-Whitney test in case of non-parametric data). This analysis will be a

comparative analysis and will be done on eligible population of patients without protocol violation and who have at least one treatment dose and an evaluable primary endpoint (AST and ALT).

- Number of patients experiencing hepatic complications between the experimental arms and control arm at the end of the treatment using chi-square (Fischer for non-parametric data). This analysis will be a comparative analysis and will be done on eligible population of patients without protocol violation and who have at least one treatment dose and an evaluable primary endpoint (AST and ALT).

Exploratory Analysis:

- The mean relative change in lipid profile levels between the experimental arms and the control arm from baseline till end of treatment using T-test (Mann-Whitney test in case of non-parametric data). This analysis will be a comparative analysis and will be done on eligible population of patients without protocol violation and who have at least one treatment dose and an evaluable primary endpoint (AST and ALT).

All tests will be performed on the 5% level of significance.

Procedure for accounting for missing, unused, and spurious data will be explained in the statistical analysis plan.

Any deviation(s) from the original statistical plan will be described in the final report).

Interim analysis:

Interim analysis will be performed when all patients complete 6 months of treatment. If a statistically significant difference is observed between placebo and active arm(s), the study will be terminated for the benefit of patients who

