	
were randomly assigned to placebo arm and to rapidly disseminate evidence supporting a treatment benefit to the broader community⁵.

Estimate Duration of the Study
	
 • Protocol Planned Date: October 2018 • First Patient In (FPI): December 2018 • Last Patient In (LPI): March 2019 • Last Patient Out (LPO): December 2019 • Estimated enrollment duration: 3 Months • Estimate treatment duration: 9 Months • Database lock planned date: January 2020 • Estimated Report date: February 2020

⁵ Zannad F, et al. Development of Therapeutics for Heart Failure. When to Stop a Clinical Trial Early for Benefit: Lessons Learned and Future Approaches. Circulation: Heart Failure. 2012; 5: 294-302. doi: 0.1161/CIRCHEARTFAILURE.111.965707

[figure not shown]

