16.4 STATISTICAL ANALYSES

The statistical analysis of this study will consist of reporting of individual data listings, providing descriptive statistics for parameters of interest, and statistical testing of the primary and secondary variables.

The final statistical analyses will be performed when the patients on Heptex and placebo complete 9 months of treatment.

Detailed analysis methods will be provided in the statistical analysis plan.

16.4.1 Descriptive analysis:

- Percent (%) distribution for all categorical variables and mean with (SD) and median (Minimum: Maximum) for continuous variables according their distribution.

16.4.2 Primary analysis:

- The main objectives of this phase II study is to explore the anti-oxidant activity of Heptex as assessed by improvement in serum aspartate aminotransferase (AST) and alanine aminotransferase (ALT) levels by measuring:
- The mean relative change in ALT & AST levels between the experimental arms and the control arm from baseline till end of treatment using T-test (Mann-Whitney test in case of non-parametric data). This analysis will be a comparative analysis and will be done on eligible population of patients without protocol violation and who have at least one treatment dose and an evaluable primary endpoint (AST and ALT).
- Number of patients with normal ALT & AST at end of treatment between the experimental arms and the control arm. The cut-off values of ALT were 0-43 IU/L and of AST were 0-40 IU/L⁸ using chi square (Fischer test for non-parametric data). This analysis will be comparative analysis and will be conducted on the eligible population of patients without protocol deviation, who have at least one treatment dose and an evaluable primary endpoint (ALT and AST).

All tests will be performed on the 5% level of significance.

⁸ Uslusoy H, Nak S, Gülten M, Bıyıklı Z. Non-alcoholic steatohepatitis with normal aminotransferase values. World Journal of Gastroenterology. 2009;15(15):1863.

Procedure for accounting for missing, unused, and spurious data will be explained in the statistical analysis plan.

Any deviation(s) from the original statistical plan will be described in the final report).

16.4.3 Secondary analysis:

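### The 6-month efficacy stop names no endpoint, dose rule or boundary, and the same endpoints are tested again at 9 months at an unadjusted 5%

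*Protocol*

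**What the plan says.** - **Timing and rule.** Protocol section 16.4.5 and the synopsis state: "Interim analysis will be performed when all patients complete 6 months of treatment". The rule follows: "If a statistically significant difference is observed between placebo and active arm(s), the study will be terminated". The reasons given are the interest of placebo patients and the wish "to rapidly disseminate evidence supporting a treatment benefit to the broader community".
- **Level.** The only level for testing, in section 16.4.2 and in the synopsis, is: "All tests will be performed on the 5% level of significance". No exception is made for the interim.
- **Two looks at the same endpoints.** Section 16.3 opens: "During interim analysis (at 6 months of treatment) and final analysis at the end of treatment, the following endpoints will be evaluated". The list that follows holds the primary, secondary and exploratory (lipid) endpoints. Section 16.4 adds: "The final statistical analyses will be performed when the patients on Heptex and placebo complete 9 months of treatment".
- **Second statement of the rule.** Section 19 has "If results of interim analysis show a statistically significant difference between placebo and active arms (in favor of active arm"), after which the study is again to be terminated. That bullet stands in a list introduced by "The sponsor may discontinue the study or close-out a site in some cases".
- **Sample size.** Section 16.1 uses alpha 5% described as one-sided, 80% power and an effect size of 0.63. It gives 43 evaluable and 47 randomised patients per arm, with no allowance for an interim look.

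**The concern.** Two separate faults meet in this rule.

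First, the trigger is undefined. The rule does not say which of the endpoints in section 16.3 counts, whether one significant test is enough, or whether one dose is enough (16.4.5 makes the plural of arm optional, section 19 uses the plural).

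Second, the interim and final analyses each appear to spend the full 5%, so even a single comparison exceeds its nominal error.

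The stakes are more than nominal. A positive interim ends the trial and is to be made public as evidence of benefit. If an inactive product can meet the rule fairly often, that is the finding most likely to mislead. The gain for placebo patients is small, because the rule cannot act until the last patient has reached 6 months.

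Two smaller wording points need aligning. Section 19 states the direction, which 16.4.5 only implies through its benefit clause. Section 19 also opens permissively, where 16.4.5 is mandatory.

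**Working it through.** **1. The plan's own figure.** Inputs from 16.1: effect size 0.63, 43 per arm, Mann-Whitney test. The method is a noncentral t with efficiency 3/pi = 0.955. The effective n is 43 x 0.955 = 41.06 per arm, and the noncentrality is 0.63 x sqrt(41.06/2) = 2.85.
- Two-sided 5%: power 80.5%, and 43 is the smallest n reaching 80%. The figure is reproduced.
- One-sided 5%, as written: power 88.2%, and 34 per arm would suffice.

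It is therefore unclear which 5% the interim would use, and both are shown below.

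**2. One comparison, two looks, no true effect.** The overall error is 1 - P(no rejection at 6 months and none at 9 months), with bivariate normal test statistics. The correlation between looks is not in the protocol and is assumed to be 0.5 to 0.9. If the looks were independent, the error would be 1 - 0.95^2 = 9.75%.

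| Correlation between looks | 0.5 | 0.65 | 0.8 | 0.9 |
|---|---|---|---|---|
| Two-sided 5% at both looks | 9.07% | 8.56% | 7.81% | 7.04% |
| of which in favour of active (nominal 2.5%) | 4.54% | 4.28% | 3.90% | 3.52% |
| One-sided 5% at both looks | 8.78% | 8.25% | 7.52% | 6.81% |
| ALT change, either of two doses, two-sided 5%, in favour of active | 8.09% | 7.63% | 6.97% | 6.30% |

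The last row uses a correlation of 0.5 between doses, from the shared placebo arm at 1:1:1.

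**3. Several primary tests.** Per look there are 2 doses x 2 enzymes x 2 forms (change, normalisation) = 8 tests. There are 6 if normalisation means both enzymes normal: 2 x 2 change tests plus 2 x 1 normalisation tests. These were simulated under no effect with 3 arms of 43, 24 settings and 20,000 trials each, using t-tests on change and chi-square on normalisation. Only results in favour of active were counted. Assumed: look correlation 0.5-0.9, ALT-AST correlation 0.6-0.8, 15-50% normalising.

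| Trigger | False stop at 6 months | False favourable result at either look |
|---|---|---|
| Any of 6 tests, two-sided 5% | 9.2-11.7% | 13.0-19.7% |
| Any of 8 tests, two-sided 5% | 10.3-13.4% | 14.7-22.6% |
| Any primary test, one-sided 5% | 16-23% | 22-37% |
| All three tests for a dose, two-sided 5% | 0.3-1.2% | not computed |
| All four tests for a dose, two-sided 5% | 0.1-0.7% | not computed |

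From the nominal 2.5%, the extra tests add 9.2 - 2.5 = 6.7 to 13.4 - 2.5 = 10.9 points. The second look adds a further 3.7 to 9.6 points within individual settings. Letting secondary or lipid tests trigger the stop would raise the rates further.

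**4. What an early stop saves.** Assume uniform accrual over the 12 weeks. The last patient reaches week 24 at study week 36. A patient who entered at week u then has u of 36 weeks left, a mean of 6. With an analysis lag of L weeks the mean is (12 - L)^2/24: 100/24 = 4.2 weeks for L = 2, and 36/24 = 1.5 weeks for L = 6.

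**5. A boundary that works.** Two-sided p<0.001 at 6 months and p<0.049 at 9 months sum to 0.05, so the error for one comparison cannot exceed 5% at any correlation. At 0.5/0.65/0.8/0.9 it is 4.96/4.93/4.91/4.90%. Halved for two doses (0.0005 and 0.0245), the two-sided error over both doses and looks is 4.62-4.56%.

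**The case against.** - **The interim level is inferred.** The 5% sentence sits under the primary analysis, 16.4.5 gives no level, and detailed methods are left to the SAP. That is fair as far as it goes. But the sentence covers all tests, and the stop is already fixed in the protocol. An SAP boundary stricter than 5% would conflict with that text unless the protocol is amended.
- **The stop may not be mandatory.** Section 19 introduces its list permissively. Its own bullet, like 16.4.5 and the synopsis, nevertheless says the study will end. The passages need aligning, but the permissive lead-in does not remove the rule.
- **The test count may be too high.** Normalisation is defined at end of treatment, so it arguably has no 6-month form. With only the four change tests, the false stop is about 7-8% and the false favourable rate over both looks about 10-14%. This is a legitimate reading, and it lowers the multi-test figures. Section 16.3 does, however, list normalisation for the interim, and the error stays well above nominal either way.
- **This is an exploratory phase II trial.** Strict error control over every primary test at the final analysis is partly a matter of preference, and the core point does not depend on it. The argument is weaker for a rule that ends the trial and announces a benefit.
- **The cost.** Splitting alpha over two doses does lower power. This stands, and the cost is given with the remedy.

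**Conclusion.** The concern holds and should be fixed before the interim analysis. The firmest figure is for one comparison: 7.0-9.1% two-sided, or 6.8-8.8% if the 5% is one-sided, over look correlations of 0.9 to 0.5. Inflation is present across that whole range.

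Beyond that, the error depends on how the trigger is read. At two-sided 5% the false stop at 6 months runs from about 1% or less (all tests for a dose) to between 1 in 11 and 1 in 7 (any of 6 to 8 primary tests). On the any-test reading, a false favourable result at one look or the other occurs in 1 in 8 to 1 in 4 trials. A stopping rule whose error varies this much with an unstated definition is not usable as written. The multi-test figures rest on assumed correlations and normalisation rates. The wording conflicts between 16.4.5 and section 19 are minor by comparison.

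**What to change.** Choose one option and apply it in the synopsis, 16.4.5 and section 19 alike.

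**Option 1.** Delete the efficacy stop and state that the 6-month results are descriptive. No alpha is spent, and little placebo exposure is forgone.

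**Option 2.** Keep a stop, limited to one named endpoint (ALT change, the sample-size variable), in favour of active. State the sidedness, whether one dose is enough, and a boundary, for example two-sided p<0.001 then p<0.049. If either dose may trigger, use Dunnett or Holm, or halve both levels. A simple split is safer here than a boundary built on an information fraction, because the same patients contribute at both looks and the correlation is unknown.

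Either option controls error for ALT change only. It is advisable, though a separate matter, to rank AST change and normalisation below it in 16.3.1 or label them supportive. Six to eight primary tests at two-sided 5% give a false favourable result in 9.1-13.4% of trials at the final look alone.

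**Cost.** The edits are to wording in those sections, 16.3.1 and the SAP.
- Using 0.049 at the final look costs about 0.2 points of power (80.5% to 80.3%).
- An early stop becomes less likely. If the 0.63 effect is already present at 6 months (assumed), the chance per dose of crossing falls from about 80% to about 30% at 0.001, or 23% at 0.0005.
- Halving for two doses lowers per-dose power at 43 per arm from 80.5% to about 71% if tests are two-sided, or from 88% to about 80% if one-sided 5% applies. Under the two-sided reading the stated 80% must be restated, or about 52 evaluable patients per arm would be needed to keep it. Dunnett or Holm lose less.
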